1.0 Objectives

1.1 Describe the purpose, specific aims, or objectives of this research.

Response: To study the effects of transcranial direct current stimulation (tDCS) on weight and appetite.

Aim:

- 1. To compare weight loss over one month in active tDCS group with sham tDCS group. We will measure weight of every participants at the beginning of the study and one month after the last session of tDCS*
- 2. To compare change in insulin sensitivity over one month in active tDCS group with sham tDCS group. We will measure fasting insulin and glucose level, and calculate homeostatic model assessment-insulin resistance (HOMA-IR)*
- 3. To compare change in cognitive performance as a response to food over one month in active tDCS group with sham tDCS group. We will evaluate performance in a computerized task that measures executive functions under the presence of food (working memory, inhibitory control and a combination of both). We will assess changes in accuracy and speed in the task under active tDCS versus sham tDCS.*
- 4. To compare change in post-prandial glucose excursion and average meal counts per day. We will use continuous glucose monitor to record the frequency and amplitude of glucose excursion.*

1.2 State the hypotheses to be tested, if applicable.

NOTE: A hypothesis is a specific, testable prediction about what you expect to happen in your study that corresponds with your above listed objectives.

Response:

Hypothesis:

- 1. Active tDCS will result in more weight loss, appetite reduction and improved insulin sensitivity compared with sham tDCS over one month period.*
- 2. The effect of tDCS on weight, appetite, glucose tolerance and cognitive response to food varies according to the underlying allele status of BDNF and COMT gene*

2.0 Scientific Endpoints

2.1 Describe the scientific endpoint(s), the main result or occurrence under study.

*NOTE: Scientific endpoints are outcomes defined before the study begins to determine whether the objectives of the study have been met and to draw conclusions from the data. Include primary and secondary endpoints. Some example endpoints are: reduction of symptoms, improvement in quality of life, or survival. Your response should **not** be a date.*

Response:

Primary endpoints: change in weight, measured as a percentage of baseline body weight.

Secondary endpoints: change in HOMA-IR, change in average daily meal counts based on frequency of glucose excursion on continuous glucose monitor, change in average amplitude of glucose excursion curve after meals, change in cognitive performance in response to food

3.0 Background

3.1 Provide the scientific or scholarly background, rationale, and significance of the research based on the existing literature and how it will contribute to existing knowledge. Describe any gaps in current knowledge. Include relevant preliminary findings or prior research by the investigator.

Response:

Transcranial Direct current stimulation (tDCS) is a procedure in which a pair of electrode pads is applied over the scalp to deliver mild direct electric current to a specific area of the brain. It changes spontaneous firing rate of neurons underlying the pads[1], and the persistence of this modification in excitability of neurons can last up to 1 hour after the cessation of electric current[2]. This effect can be prolonged with repetitive stimulation over several consecutive days, most likely mediated by synaptic changes[3].

Left dorsolateral prefrontal cortex is a subregion of the prefrontal cortex considered to be involved in taste[4] and satiation[5]. Previous studies also demonstrated left dorsolateral prefrontal cortex in response to meal is different in lean men and women from obese subjects[6, 7], with obese subjects mounted a more significant response after meal. Therefore, this region of brain is a potential target for obesity intervention.

A recent study showed that tDCS inhibit craving for food[8]. Another prospective study of 9 obese subjects reveal that tDCS is associated with weight loss[9]. Our proposed study will explore the effect of tDCS on weight, appetite and glucose tolerance in long term (over 1 month period) and in a larger study population. We will apply sham tDCS as control. In sham tDCS, the duration of stimulation will be limited to 15 seconds instead of 30 minutes in the active tDCS group. According to previous study, subjects are the not able to differentiate sham from active tDCS [9].

Polymorphism of the catechol-O-methyltransferase (COMT) gene was found to interact with tDCS intervention and change its effect on higher level executive function[10]. The brain derived neurotrophic factor (BDNF) gene polymorphism was also shown to modulate the effect of tDCS on motor cortex plasticity [11]. Therefore, these genes can potentially alter the effect of tDCS on weight, appetite and cognitive response to food.

3.2 Include complete citations or references.

Response:

1. *Wassermann, E.M. and J. Grafman, Recharging cognition with DC brain polarization. Trends Cogn Sci, 2005. 9(11): p. 503-5.*

4.0 Study Design

- 4.1 *Describe and explain the study design (e.g. case-control, cross-sectional, ethnographic, experimental, interventional, longitudinal, observational).*

Response:

Single center, double blinded, controlled, randomized, prospective study

There are two groups to which participants are being randomized, one with active transcranial stimulation and one with sham stimulation.

5.0 Local Number of Subjects

5.1 *Indicate the total number of subjects that will be enrolled or records that will be reviewed locally.*

Response:

20

5.2 *If applicable, indicate how many subjects you expect to screen to reach your target sample (i.e. your screen failure rate).*

Response:

40

5.3 *Justify the feasibility of recruiting the proposed number of eligible subjects within the anticipated recruitment period. For example, how many potential subjects do you have access to? What percentage of those potential subjects do you need to recruit?*

Response:

In our clinics, we will see about 20 patients every week that meet the inclusion criteria. We only need to recruit 10% of them over 10 weeks.

6.0 Inclusion and Exclusion Criteria

6.1 *Describe the criteria that define who will be **included** in your final study sample.*

NOTE: This may be done in bullet point fashion.

Response:

1. Men and women 18 to 80 years of age
2. Body mass index > 30 kg/m²

6.2 *Describe the criteria that define who will be **excluded** from your final study sample.*

NOTE: This may be done in bullet point fashion.

Response:

1. Current participation in any other concurrent clinical trials or previous participation within 30 days before the screening visit
2. Pregnancy or premenopausal women who are trying to be pregnant
3. Patients who are incompetent to give consent
4. Obesity due to a known secondary cause (Cushing's syndrome, hypothyroidism, etc) or a history of weight loss surgery

5. Have taken any of the following medications within the past 3 months:
phentermine, naltrexone, bupropion, topiramate, lorazepam, phendimetrazine, methamphetamine, benzphetamine, diethylpropion

6. Any contraindication to receive transcranial direct current stimulation (tDCS):

- Personal or family history of seizures, epilepsy or other unexplained loss of consciousness.
- Current or past history of skin disease or damaged skin on the scalp at the site of stimulation (i.e. eczema, skin with ingrown hairs, acne, razor nicks, wounds that have not healed, recent scar tissue, broken skin, etc.).
- Prior neurosurgical procedure or radiation.
- Known diagnosis of brain lesions, such as tumor, stroke or multiple sclerosis
- Implanted pacemaker, medication pump, vagal stimulator, deep brain stimulator, Transcutaneous Electrical Nerve Stimulation unit, ventriculo-peritoneal shunt or any metallic implant on the head.

6.3 *Indicate specifically whether you will include any of the following special populations in your study using the checkboxes below.*

NOTE: Members of special populations may not be targeted for enrollment in your study unless you indicate this in your inclusion criteria.

Response:

- Adults unable to consent
- Individuals who are not yet adults (infants, children, teenagers)
- Pregnant women
- Prisoners

6.4 *Indicate whether you will include non-English speaking individuals in your study. Provide justification if you will exclude non-English speaking individuals.*

In order to meet one of the primary ethical principles of equitable selection of subjects, non-English speaking individuals may not be routinely excluded from research as a matter of convenience.

In cases where the research is of therapeutic intent or is designed to investigate areas that would necessarily require certain populations who may not speak English, the researcher is required to make efforts to recruit and include non-English speaking individuals. However, there are studies in which it would be reasonable to limit subjects to those who speak English. Some examples include pilot studies, small unfunded studies with validated instruments not available in other languages, studies with numerous questionnaires, and some non-therapeutic studies which offer no direct benefit.

Response:

We will not enroll non-English speaking individuals. Enrollment in this study is not large (20 participants in total) and there is no reason to believe that the study would be withholding benefit from non-English speaking subjects.

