9.0 Recruitment Methods

N/A: This is a records review only, and subjects will not be recruited.

NOTE: If you select this option, please make sure that all records review procedures and inclusion/exclusion screening are adequately described in other sections.

9.1 *Describe when, where, and how potential subjects will be recruited.*

NOTE: Recruitment refers to how you are identifying potential participants and introducing them to the study. Include specific methods you will use (e.g. searching charts for specific ICD code numbers, Research Participant Groups, posted advertisements, etc.).

Response:

Participants will be identified by prescreening clinical charts prior to their clinic visit, and patient doctor interaction at the time of their visit at the Diabetes Endocrinology Center of WNY and Western New York VA Hospital. If the patient expresses interest after speaking with their physician and provide their contact information, they will be scheduled for a screening visit. The recruitment will start immediately after approval by IRB. Advertisements and flyers will be posted at these locations with the contact phone number for the patient to call the research team, if interested in participating.

Locations include:

1. [name]
2. [name]

3. [name]

4. [name]

9.2 *Describe how you will protect the privacy interests of prospective subjects during the recruitment process.*

NOTE: Privacy refers to an individual's right to control access to him or herself.

Response: HIPAA waiver is being requested, so that we will be able to use identifiable health information for subject recruitment. Any potential participant's personal health information will be kept solely between the study team and handled just as clinic patients' personal health information is handled. Locked file cabinets in locked offices for written data, password protected logins for electronic data, private rooms for any patient discussion. The data will only be shared with the study team who have all taken CITI training and will follow University privacy policies. We will not retain personal identifiers once the candidate is identified in the electronic medical record and contacted, no matter if the candidate agrees or declines to participate.

9.3 *Identify any materials that will be used to recruit subjects.*

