10.0 Procedures Involved

10.1 *Provide a description of all research procedures or activities being performed and when they are performed once a subject is screened and determined to be eligible. Provide as much detail as possible.*

NOTE: This should serve as a blueprint for your study and include enough detail so that another investigator could pick up your protocol and replicate the research. For studies that have multiple or complex visits or procedures, consider the addition of a schedule of events table in in your response.

Screening Day

All subjects will have completed the following procedures prior to participating in the study:

- 1) Informed consent
- 2) Medical history
- 3) Physical exam (including body mass index measurement)

We will collect general demographic data regarding years of education, race/ethnicity.

A continuous glucose monitor will be calibrated with finger blood glucose result and the probe of the monitor will be inserted into the abdominal subcutaneous tissue. Patient will be instructed on how to use continuous glucose monitor, they will be instructed to wear it and document the time and the types of food of every meal for at least 72 hours after the screening visit.

Subjects will be instructed not to change their medications during the whole study period and not to take insulin for at least 4 hours before visit 1, visit 5 and visit 6.

Visit 1:

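### Exclusion item 5 is a closed list of nine drugs, so a patient still losing weight on an unlisted weight-loss drug can enter a trial whose primary endpoint is percent weight change

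*Combined protocol and SAP*

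**What the plan says.** Section 6.2, item 5, excludes patients who "Have taken any of the following medications within the past 3 months", and then names nine: "phentermine, naltrexone, bupropion, topiramate, lorazepam, phendimetrazine, methamphetamine, benzphetamine, diethylpropion". Nothing follows the list: no drug class, no wording that makes the names examples, and no reason for the item or for any entry.

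The only other weight-related exclusion is item 4: "Obesity due to a known secondary cause (Cushing's syndrome, hypothyroidism, etc) or a history of weight loss surgery". It does not reach medication.

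During the study, section 10.1 says: "Subjects will be instructed not to change their medications during the whole study period". The same sentence tells them "not to take insulin for at least 4 hours before visit 1, visit 5 and visit 6", so patients on glucose-lowering treatment are expected among those enrolled.

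Recruitment in section 9.1 is by chart review and "patient doctor interaction at the time of their visit at the Diabetes Endocrinology Center of WNY and Western New York VA Hospital". Section 2.1 gives the endpoint: "Primary endpoints: change in weight, measured as a percentage of baseline body weight". The secondary endpoints include HOMA-IR, meal counts and the amplitude of glucose excursions.

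Section 10.1 randomizes in blocks of 10 and states no stratification factor. The covariates that section 17.1 proposes for checking baseline imbalance are age, gender, the two gene markers and the baseline values of the outcomes. Medication is not among them.

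**The concern.** A screener will apply item 5 as written. Someone who began a weight-loss drug outside the nine names shortly before screening passes, enrols, and is then told to carry on with it. Their weight may go on falling for reasons unrelated to stimulation, and the primary endpoint cannot tell the two causes apart. With 20 subjects, a handful of such patients adds noise, and an uneven split between the arms can look like a treatment effect or hide one. Since medication use is not a planned covariate, the analysis as written would not show this.

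A second, independent point is that lorazepam appears in the list without explanation. A reader cannot tell whether the entry is intended or what rule it serves.

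**Working it through.** There is no figure in the plan to reproduce: sections 17.1 and 17.2 give no effect size, standard deviation or power. The main check is textual, followed by an illustration of size.

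**Textual check: does anything stop a recent starter of an unlisted weight-loss drug?**

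1. Section 6.1 requires only age 18 to 80 and BMI above 30. The patient passes.
2. Section 6.2, item 5, reaches nine names only. The patient passes.
3. Section 6.2, item 4, reaches secondary obesity and surgery. The patient passes.
4. The remaining items (other trials, pregnancy, consent, stimulation contraindications) do not concern weight-affecting drugs. The patient passes.
5. The section 10.1 medication instruction restricts changes after entry. It does not remove a drug already being taken.
6. Randomization is not stratified on medication, and section 17.1 does not list it as a covariate.

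**Length of exposure.** Visit 1 falls within 2 weeks of screening (up to 14 days), visits 1 to 5 are on consecutive days (4 days), and visit 6 is 4 weeks later (28 days). From visit 1 to visit 6 is 4 + 28 = 32 days. From screening it is up to 14 + 32 = 46 days. Section 10.2 lists weight at screening, visit 5 and visit 6, so if the screening weight is the baseline, loss before the first stimulation also counts. Section 19.2 says weight is monitored at every visit, so a visit 1 weight may exist.

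**Illustration of size.** Inputs: total of 20 (section 5.1); 10 per arm (assumption, since the allocation ratio is not stated); k users of an unlisted weight-active drug (assumption, 2 to 8); effect e of the drug on percent weight change over the study (assumption, 1 to 3 points). The two-block structure is ignored.

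The chance that exactly a of the k users fall in the active arm is C(k,a) × C(20−k,10−a) / C(20,10), with C(20,10) = 184,756. The arms differ by |2a − k| users. For k = 4, an even split has probability 6 × 12,870 / 184,756 = 0.418, so a difference of 2 or more has probability 0.582. A difference of 4 has probability 2 × 8,008 / 184,756 = 0.087.

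| Users among 20 | Arms differ by 2 or more | Arms differ by 4 or more |
|---|---|---|
| 2 | 47% | 0% |
| 4 | 58% | 9% |
| 6 | 63% | 14% |
| 8 | 65% | 17% |

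The shift in the between-arm mean is e × d / 10 for a difference of d users:

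- d = 2: 1 × 2/10 = 0.2 to 3 × 2/10 = 0.6 points.
- d = 4: 1 × 4/10 = 0.4 to 3 × 4/10 = 1.2 points.

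The shift can go in either direction and averages zero over randomizations.

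**The case against.** The strongest case for the plan has four parts.

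- **Medications are held constant.** The section 10.1 instruction is a real safeguard against new starts and dose changes, and a subject at stable weight on a long-held drug adds little to percent change from baseline. This stands, and it narrows the problem to drugs begun before screening whose effect is still running.
- **Assignment is randomized.** A reader might infer that unlisted drugs confound or bias the comparison. They do not do so systematically: use that precedes randomization is balanced in expectation, and an additive drug effect does not shrink the expected difference. What remains is variance and chance imbalance, which matter more with about 10 per arm.
- **Baseline imbalance is already to be examined.** Section 17.1 plans sensitivity analyses for imbalance and outliers, and section 10.1 takes a medical history. The screening forms are not in the public document and may record medication. Even so, medication is not a named covariate.
- **Nobody knows how many users there are.** The documents give no prevalence. A diabetes and endocrinology clinic makes such patients plausible, but that is not a count.

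On lorazepam, a reader might infer a slip for a similarly named weight-loss drug, or think the entry is what opens the gap. The documents support neither. The protocol never says that item 5 is limited to weight-loss drugs, and a deliberate exclusion of a centrally acting drug is possible in a brain-stimulation study with cognitive endpoints. The gap comes only from the closed form of the list. All that can be said is that the entry has no stated reason.

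**Conclusion.** The point holds. As written, the criteria admit a patient actively losing weight on an unlisted weight-loss drug, and neither the allocation nor the planned analysis takes account of it. The consequence is added variance and possible chance imbalance in a small trial, not systematic bias.

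The size cannot be established. The illustrative shifts of 0.2 to 0.6 points (two-user difference) and 0.4 to 1.2 points (four-user difference) rest on 1:1 allocation, an assumed number of users and an assumed drug effect. It is tempting to call such shifts as large as the small effect mentioned in section 17.2, but that section gives no number, so the comparison cannot be made.

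The closed list deserves correction because it changes who enrols and what can be adjusted for. The lorazepam entry alone is a minor query.

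**What to change.** 1. Reword item 5 by purpose: exclude any medication taken for weight loss within the 3-month window already stated, with the named drugs as examples.
2. Confirm or correct the lorazepam entry. If it is kept for a reason other than weight, state that reason.
3. Have the sponsor decide and state how drugs taken for other reasons that also affect weight are handled. Which drugs, and on what conditions, is a clinical choice for the sponsor.
4. Record concomitant medication before randomization, if the screening form does not already do so, and add baseline use of weight-affecting drugs to the section 17.1 imbalance covariates.

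The cost is one reworded criterion, at most one more form field, one more covariate in a sensitivity analysis, and a slightly smaller recruitment pool. Section 5.3 counts about 20 patients a week and needs 10% of them over 10 weeks (20 × 10 × 0.10 = 20). That weekly figure refers to patients meeting the inclusion criteria, before exclusions, so the margin is smaller than it looks and should be rechecked after the rewording.

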7.0 Vulnerable Populations

If the research involves special populations that are considered vulnerable, describe the safeguards included to protect their rights and welfare.

NOTE: You should refer to the appropriate checklists, referenced below, to ensure you have provided adequate detail regarding safeguards and protections. You do not, however, need to provide these checklists to the IRB.

7.1 *For research that involves **pregnant women**, safeguards include:*

NOTE CHECKLIST: Pregnant Women (HRP-412)

Response: We will not be using subjects from vulnerable populations

N/A: This research does not involve pregnant women.

7.2 *For research that involves **neonates of uncertain viability or non-viable neonates**, safeguards include:*

NOTE CHECKLISTS: Non-Viable Neonates (HRP-413), or Neonates of Uncertain Viability (HRP-414)

Response:

N/A: This research does not involve non-viable neonates or neonates of uncertain viability.

7.3 *For research that involves **prisoners**, safeguards include:*

NOTE CHECKLIST: Prisoners (HRP-415)

Response:

N/A: This research does not involve prisoners.

7.4 *For research that involves **persons who have not attained the legal age for consent to treatments or procedures involved in the research (“children”)**, safeguards include:*

NOTE CHECKLIST: Children (HRP-416)

Response:

N/A: This research does not involve persons who have not attained the legal age for consent to treatments or procedures (“children”).

7.5 *For research that involves **cognitively impaired adults**, safeguards include:*

NOTE CHECKLIST: Cognitively Impaired Adults (HRP-417)

Response:

N/A: This research does not involve cognitively impaired adults.

7.6 *Consider if other specifically targeted populations such as students, employees of a specific firm, or educationally or economically disadvantaged persons are vulnerable. Provide information regarding their safeguards and protections, including safeguards to eliminate coercion or undue influence.*

Response:

Not applicable

